8.4.5 Analyses of Vital Signs

Systolic and diastolic blood pressure and heart rate will be summarized using descriptive statistics at each scheduled visit.

8.4.6 Analyses of Anti-AMG 145 Antibody Formation

The **development of** anti-AMG145 antibodies (binding and neutralizing) at anytime will be **reported**.

8.4.7 Exposure to Investigational Product

Descriptive statistics will be produced to describe the patient-month exposure to investigational product, by treatment group for both the ICOAS and IAAS sets as well as overall. Exposure definitions are provided in [Section 5.3](#).

8.4.8 Exposure to Concomitant Medications of Interest

The number and proportion of subjects receiving the **lipid regulating** medications of interest at Study Day 1 and post-Study Day 1 will be summarized by category and preferred term for each treatment group as coded by the World Health Organization Drug (WHODRUG) dictionary.

9. Literature Citations / References

Alberti KGMM et al. Harmonizing the Metabolic Syndrome: A Joint Interim Statement of the International Diabetes Federation Task Force on Epidemiology and Prevention; National Heart, Lung, and Blood Institute; American Heart Association; World Heart Federation; International Atherosclerosis Society; and International Association for the Study of Obesity. *Circulation*. 2009;120:1640-1645.

Grundy SM et al. Diagnosis and Management of the Metabolic Syndrome: An American Heart Association/National Heart, Lung, and Blood Institute Scientific Statement. *Circulation*. 2005;112:2735-2752.

10. Appendices

Appendix A. Analytical Study Week Assignments

Selected endpoints will be summarized by scheduled study visits in descriptive analyses. Since the actual visits may not exactly coincide with their scheduled visit day, the actual visit day is mapped to the study visit generally by non-overlapping consecutive intervals covering the entire time continuum, with scheduled visit time being the center of each interval. The mapping intervals for all distinct schedules are summarized in the following tables. **Week 0 mapping does not pertain to parent study week mapping. Data from the parent studies will use the original analytical weeks in the individual study SAPs.**

Handling multiple records assigned to an analytical study week:

If there is more than one record in a study week interval, the analytical record for that specific study week will be defined as the record closest to the scheduled study day of that specific study week ($7 \times \text{study week} + 1$). If two records are equidistant from the scheduled day, then the earlier record will be chosen. If there are multiple records on the same day, the last record will be used.

Scheduled Visit Week	Vital Signs for AMG 145+SOC group	Vital signs for SOC-only group
Week 0	≤ 1	≤ 1
Week 2	(1, 21]	
Week 4	(21, 42]	
Week 8	(42, 70]	
Week 12	(70, 126]	(1, 126]
Week 24	(126, 210]	(126, End of SOC-controlled period]
Week 36	(210, 280]	
Week 44	(280, 315]	
Week 46	(315, End of SOC-controlled period]	

Scheduled Visit Week	Vital Signs for AMG 145+SOC randomized group	Vital signs for SOC Alone
Week 48	[Beginning of All-IP period, 420]	[Beginning of All-IP period, 343]
Week 50		(343, 357]
Week 52		(357, 378]
Week 56		(378, 406]
Week 60		(406, 462]
Week 72	(420, 546]	(462, 546]
Week 84	(546, 630]	(546, 630]
Week 96	(630, 686]	(630, 686]
Week 100	(686, 707]	(686, 707]
Week 102	(707, 721]	(707, 721]
Week 104	>721	>721

Scheduled Visit Week	Subjects randomized to AMG 145 or Subjects randomized to SOC that were randomized to AMG 145 in parent study		
	Fasting plasma lipids, ApoA1, ApoB, Vitamin E , Chemistry, Hematology, Anti-AMG 145 antibodies, Urinalysis, Urine microalbumin	HbA1c	Body Weight, hsCRP
Week 0	≤ 1	≤ 1	≤ 1
Week 12	(1, 126]	(1, 126]	
Week 24	(126, End of SOC-Controlled period]	(126, End of SOC-Controlled period]	
Week 48	[Beginning of All-IP period, 420]	[Beginning of All-IP period, 532]	[Beginning of All-IP period, 532]
Week 72	(420, 588)		
Week 96	(588, 700]		
Week 104	> 700	>532	>532

Scheduled Visit Week	Subjects randomized to SOC that were randomized to control in the parent study		
	Fasting plasma lipids, ApoA1, ApoB, Vitamin E , Chemistry, Hematology, Anti-AMG 145 antibodies, Urinalysis, Urine microalbumin	HbA1c	Body weight, hsCRP
Week 0	≤ 1	≤ 1	≤ 1
Week 12	(1, 126]	(1, 126]	
Week 24	(126, End of SOC-Controlled period]	(126, End of SOC-Controlled period]	
Week 48	[Beginning of All-IP period, 378]	[Beginning of All-IP period, 378]	[Beginning of All-IP period, 532]
Week 60	(378, 462]	(378, 574]	
Week 72	(462, 588)		
Week 96	(588, 700]		
Week 104	> 700	>574	>532

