7.1.1.18 Week 60 (\pm 7 Days)

- Vital signs: sitting blood pressure (BP), heart rate (HR)
- Review AEs/SAEs
- Review concomitant medications

- Dispense IP quantity for at-home injections
- IP reconciliation

7.1.1.19 Week 60 (\pm 7 Days)—Additional Procedures for Subjects Randomized to Placebo or SOC in Parent Study and Randomized to SOC-alone in Year 1

- Blood draw for fasting lipids (\geq 9 hour fasting sample), ApoA1, ApoB, Lp(a), Vitamin E (sample drawn, testing by reflex when LDL-C is $<$ 25 mg/dL), chemistry, and hematology
- HCV viral load (in subjects positive for HCV)
- Urine pregnancy test
- Urinalysis
- Urine microalbumin

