7.1.1.20 Week 72 (\pm 7 Days)

- Vital signs: sitting blood pressure (BP), heart rate (HR)
- Review AEs/SAEs
- Review concomitant medications
- Dispense IP quantity for at-home injections
- IP reconciliation

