7.1.1.21 Week 84 (\pm 7 Days)

- Vital signs: sitting blood pressure (BP), heart rate (HR)
- Review AEs/SAEs
- Review concomitant medications
- Urine pregnancy test
- Blood draw for fasting lipids (\geq 9 hour fasting sample), ApoA1, ApoB, Lp(a), Vitamin E (sample drawn, testing by reflex when LDL-C is $<$ 25 mg/dL), chemistry, hematology, and anti-AMG 145 antibodies
- HCV viral load (in subjects positive for HCV)
- Urinalysis
- Urine Microalbumin
- Dispense IP quantity for at-home injections
- IP reconciliation

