7.1.1.22 Week 96 (\pm 7 Days)

- Vital signs: sitting blood pressure (BP), heart rate (HR)
- Review AEs/SAEs
- Review concomitant medications
- Dispense IP quantity for at-home injections

- IP reconciliation

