Title: A Multicenter, Controlled, Open-label Extension (OLE) Study to Assess the Long-term Safety and Efficacy of AMG 145

Amgen Protocol Number:20120138

EudraCT Number: **2012-004357-83**

OSLER 2

Open Label Study of Long Term Evaluation Against LDL-C Trial

Amendment 4 Date: 15 April 2014

Rationale:

This document provides the rationale and detailed list of changes for Amendment 4, dated 15 April 2014, from superseding amendment 3 of the study protocol, dated 24 February 2014.

The purpose of the amendment is to:

- Update the schedule of assessments schema for clarification and ease of use
- Add a patient questionnaire for patients experiencing a change in the device used to deliver AMG 145
- Minor other updates, clarifications and corrections

Amendment 3

Title: A Multicenter, Controlled, Open-label Extension (OLE) Study to Assess the Long-term Safety and Efficacy of AMG 145

Amgen Protocol Number: 20120138
EudraCT Number: 2012-004357-83

OSLER 2

Open Label Study of Long Term Evaluation Against LDL-C Trial

Goal Achievement after Utilizing an anti-PCSK9 antibody in Statin Intolerant Subjects

Amendment Date: 15 November 2013

Superseding Amendment Date: 15 February 2014

Superseding Amendment Date: 24 February 2014

Rationale:

This document provides the rationale and detailed list of changes for Amendment 3, dated 24 February 2014, from superseding amendment 2 of the study protocol, dated 23 May 2013.

The purpose of the amendment is to:

- Add Vitamin E reflex testing to the protocol in cases where LDL-C is < 25 mg/dL.
- Add language for the use of the 3.5 mL personal injector. The 3.5 mL Personal Injector will only be made available for use in this study once it has been determined that the intended user population for AMG 145 can safely and effectively use the device in clinical trials under guidance of study investigators.
- The schedule of assessments and schema were clarified and changed in format to be easier to use
- The body of the protocol and schedule of assessments were updated and made consistent
- The visit schedule was clarified to list the exact timing of the visit, replacing reference to quarterly visits
- The protocol now references the latest IB (2013)
- The protocol now includes "Investigator Responsibilities for Data Collection"
- Non-coronary revascularizations will no longer be collected (update to be consistent with DMC charter)
- Minor other updates, clarifications and corrections

Amendment 2 - Superseding Amendment

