3.2 Secondary Endpoints

- Percent change from baseline in LDL-C at each visit with planned lipid measurements
- Change from baseline in LDL-C at each visit with planned lipid measurements
- Percent change from parent study EOS in LDL-C at each visit with planned lipid measurements
- Change from parent study EOS in LDL-C at each visit with planned lipid measurements

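### The SAP's lipid and laboratory windows have no Week 84 row, so Week 84 samples would be reported as Week 72 or Week 96

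*SAP*

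**What the plan says.** SAP Appendix A assigns each record to an analytical week "generally by non-overlapping consecutive intervals covering the entire time continuum, with scheduled visit time being the center of each interval", with the scheduled day equal to 7 × week + 1. The affected column in both laboratory tables begins "Fasting plasma lipids, ApoA1, ApoB, Vitamin E , Chemistry, Hematology" and also covers antibodies, urinalysis and urine microalbumin. Its rows after Week 48 are:

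- Randomized to AMG 145, or to SOC with AMG 145 in the parent study: Week 72 (420, 588), Week 96 (588, 700], Week 104 > 700.
- Randomized to SOC with control in the parent study: Week 60 (378, 462], Week 72 (462, 588), Week 96 (588, 700], Week 104 > 700.

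The vital-sign table in the same appendix does have a Week 84 row, (546, 630].

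Protocol 7.1.1.21 (Week 84 ± 7 days) lists a blood draw for fasting lipids, apolipoproteins, Lp(a), Vitamin E, "chemistry, hematology, and anti-AMG 145 antibodies", plus urinalysis and microalbumin. Sections 7.1.1.20 (Week 72) and 7.1.1.22 (Week 96) list no blood or urine sample. Protocol Appendix A and the antibody schedule in Section 7.3 agree.

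The SAP's first secondary endpoint (Section 3.2) is "Percent change from baseline in LDL-C at each visit with planned lipid measurements". Section 8.4.2 summarizes it for each scheduled visit.

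**The concern.** The laboratory windows are built for a sampling schedule that the protocol does not contain. A Week 84 sample taken within its visit window can never be labelled Week 84. It goes to Week 72 or Week 96 according to which side of Day 588 it falls, and on Day 588 itself it goes nowhere.

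The by-visit LDL-C table for the All-IP period would then show a Week 72 and a Week 96 result, each from part of the subjects, and no Week 84 result. A reader would take the two rows as a time course over 24 weeks. They would in fact compare earlier and later attenders at one visit. Vital signs from that same visit would appear under Week 84.

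This matters because the SAP states that it supports regulatory filings and makes by-visit LDL-C change its secondary endpoint.

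**Working it through.** **Inputs.** Scheduled day = 7 × week + 1, and the window boundaries (SAP Appendix A). Week 84 visit window of ± 7 days (Protocol 7.1.1.21).

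**Step 1: reproduce the SAP's boundaries.** The boundary between adjacent scheduled weeks a and b is 7 × (a + b)/2.

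| Pair of weeks | Calculation | Printed in SAP |
|---|---|---|
| 48, 60 | 7 × 54 = 378 | 378 |
| 48, 72 | 7 × 60 = 420 | 420 |
| 60, 72 | 7 × 66 = 462 | 462 |
| 72, 96 | 7 × 84 = 588 | 588 |
| 96, 104 | 7 × 100 = 700 | 700 |

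Every boundary is exact, so the rows are a deliberate 48/(60)/72/96/104 schedule and not damage from text extraction. The vital-sign boundaries around Week 84 also reproduce: 7 × (72 + 84)/2 = 546 and 7 × (84 + 96)/2 = 630.

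**Step 2: place the Week 84 samples.** Scheduled day = 7 × 84 + 1 = 589. Permitted days are 582 to 596, 15 in all. Both laboratory tables give the same result:

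| Days | Count | Assigned to |
|---|---|---|
| 582–587 | 6 (40%) | Week 72 |
| 588 | 1 (7%) | no window |
| 589–596 | 8 (53%) | Week 96 |

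With the bracket closed at 588, the counts are 7 (47%) and 8 (53%). An exactly on-time sample becomes Week 96. All 15 days lie inside the vital-sign Week 84 window (546, 630].

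**Step 3: allow for clustering around the target day.** Assume visits are normally distributed around Day 589, truncated at ± 7 days. The SD is an assumption, because the documents give none.

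| SD | Week 72 | No window | Week 96 |
|---|---|---|---|
| 2 days | 22.7% | 17.5% | 59.9% |
| 3 days | 30.6% | 12.7% | 56.7% |

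With the bracket closed, 40–43% fall in Week 72 and 57–60% in Week 96.

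**Step 4: size of the label error.** The scheduled day of Week 72 is 505 and of Week 96 is 673. Samples labelled Week 72 lie 582 − 505 = 77 to 587 − 505 = 82 days after that day. Samples labelled Week 96 lie 673 − 596 = 77 to 673 − 589 = 84 days before it. The protocol's visit tolerance is 7 days.

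**Step 5: HbA1c.** For SOC subjects with control in the parent study, the HbA1c column has a Week 60 window (378, 574]. Its boundaries are the midpoints 7 × (48 + 60)/2 = 378 and 7 × (60 + 104)/2 = 574. Protocol 7.1.1.19 lists the Week 60 draw as lipids, apolipoproteins, Lp(a), Vitamin E, "chemistry, and hematology", with no HbA1c. This row too stands for a draw that is not planned.

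**The case against.** The strongest reply is a version difference. The SAP is an interim plan that names Amendment 2 as its basis, and the protocol supplied is Amendment 6. The Amendment 2 schedule is not available, and the exact midpoints fit a laboratory schedule at Weeks 72 and 96 that may once have existed. Other SAP content is also older than the current protocol: it still collects non-coronary revascularizations, and it stops at Week 104. This may well explain the origin, but it does not remove the problem. Amendment 3 was made partly to "Add Vitamin E reflex testing to the protocol in cases where LDL-C is" below 25 mg/dL, and the SAP's laboratory columns already list Vitamin E. The SAP was therefore partly updated after Amendment 2 while these rows were left unreconciled.

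Four narrower points have some force.

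- A vital-sign table and a laboratory table may have different schedules, so the Week 84 vital-sign row is not by itself a contradiction. It becomes one once the protocol's Week 84 draw is set beside it, because one visit then carries two week labels.
- The bracket at 588 is probably typographical. Closing it leaves the mislabelling in place.
- No on-schedule HbA1c sample is mislabelled: Week 48 (Days 330–344) lies below 378 and Week 104 (Days 722–736) above 574. The HbA1c row is an empty visit and of small effect.
- The data cutoff is not stated, so an early cut might hold few Week 84 samples or none.

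**Conclusion.** The concern holds. Measured against the supplied protocol, every on-schedule Week 84 lipid, chemistry, hematology, antibody and urine record is mislabelled by 77 to 84 days or, on Day 588 as printed, left unassigned. Roughly 40–47% would fall in Week 72 or the gap and 53–60% in Week 96. That range covers an even spread over the 15 days and a normal spread with SD of 2 to 3 days.

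The consequence depends on the data cut containing Week 84 samples, and the number of subjects affected cannot be derived from the documents. The effect is limited to descriptive by-visit summaries. Week 48 and Week 104 LDL-C, any-time antibody incidence, worst-shift tables and CK and liver-test incidence are essentially untouched. It should be corrected before any such cut, but it does not threaten the study's main conclusions.

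**What to change.** State which protocol amendment the SAP implements, and confirm that no subject was sampled at Week 72 or 96 under an earlier schedule. Then, before any data cut that contains Week 84 data, replace the Week 72 and Week 96 laboratory rows by the SAP's own midpoint rule: 7 × (48 + 84)/2 = 462, 7 × (60 + 84)/2 = 504, 7 × (84 + 104)/2 = 658.

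| Subjects | Week 48 | Week 60 | Week 84 | Week 104 |
|---|---|---|---|---|
| No Week 60 draw | to 462 | none | (462, 658] | > 658 |
| SOC-alone, control in parent study | to 378 | (378, 504] | (504, 658] | > 658 |

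If the existing Week 48 and Week 104 boundaries should stay, merge the two rows instead: Week 84 as (420, 700] and (462, 700] respectively. Either option places all of Days 582–596 in Week 84 and covers Day 588.

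Remove the HbA1c Week 60 window, and run HbA1c Week 48 to Day 532 and Week 104 from there (7 × (48 + 104)/2 = 532), as in the other table.

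Only if this SAP is applied to third-year data:

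- Cap Week 104 at 7 × (104 + 152)/2 = 896, and add Week 152 (> 896) for fasting lipids, chemistry, hematology, antibodies, HbA1c and body weight.
- Add vital-sign windows for Weeks 116 to 152.
- ApoA1, ApoB, Vitamin E, urinalysis and microalbumin need no Week 152 row.

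The cost is an edit to the SAP appendix and reprogramming of the visit mapping. No new data are needed.

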3.3.1 Study Duration for Participants

Subjects will be enrolled into the study after completion of a qualifying AMG 145 study and signing the informed consent form (ICF) of this study. The study duration is anticipated to continue for 156 weeks (approximately 3 years). During that time subjects will visit the site multiple times.

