3.3.2 End of Study

The study will continue for 156 weeks (approximately 3 years or until the investigator's recommendation of discontinuation, Amgen's recommendation of discontinuation, the subject's decision to discontinue for any reason, or until an administrative decision is made to close the study).

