7.1.1.27 Week 152 (\pm 7 Days)

- Vital signs: sitting blood pressure (BP), heart rate (HR)
- Physical exam
- Body weight
- Review AEs/SAEs
- Review concomitant medications
- Blood draw for fasting lipids (\geq 9 hour fasting sample), chemistry, hematology, anti-AMG 145 antibodies, HbA1c, coagulation
- Urine pregnancy test
- HCV Viral load (in subjects positive for HCV)
- IP reconciliation

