10.1.2 Secondary Endpoints

- Percent change from baseline in LDL-C at Week 48 and Week 104
- Change from baseline in LDL-C at Week 48 and Week 104

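### SAP Appendix A leaves every Week 104 window open-ended, so at any cutoff with data after Week 104 a Week 152 draw can be reported as Week 104

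*SAP*

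**What the plan says.** **SAP.** Appendix A sets out its windows as consecutive intervals, generally "with scheduled visit time being the center of each interval". The last row in each table is Week 104, and none has an upper limit:

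- lipids, ApoA1, ApoB, Vitamin E, chemistry, hematology, antibodies, urinalysis and microalbumin: after Day 700
- vital signs: after Day 721
- HbA1c: after Day 532, or after Day 574 for SOC subjects who had control in the parent study
- body weight and hsCRP: after Day 532

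If a window holds more than one record, "the analytical record for that specific study week will be defined as the record closest to the scheduled study day", which is 7 × week + 1. Section 7.3.2 rules out imputation of missing lipid values. Section 5.1 ends the All-IP period at the earlier of end of study and data cutoff, so nothing in the SAP excludes third-year data. The SAP's LDL-C secondary endpoint (Section 3.2) is "Percent change from baseline in LDL-C at each visit with planned lipid measurements".

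**Protocol.** Section 3.3.2 states: "The study will continue for 156 weeks". Vital signs are taken at Weeks 116, 128, 140 and 152. Section 7.1.1.27 (Week 152) lists "Blood draw for fasting lipids" together with "chemistry, hematology, anti-AMG 145 antibodies, HbA1c, coagulation", and also body weight. Section 10.1.2 names "Percent change from baseline in LDL-C at Week 48 and Week 104" as a secondary endpoint.

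**The concern.** An open-ended last window is harmless while it belongs to the last visit. The current protocol has four site visits after Week 104, and the SAP table has no row for any of them. Every third-year record therefore falls into Week 104, and the closest-record rule decides what happens to it.

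- **No closer record.** A subject without a Week 104 draw is given the Week 152 value under a Week 104 label. In effect a missing value is filled from about 48 weeks later, which sits badly with the no-imputation rule and with centring windows on the visit. It would happen only in subjects who missed Week 104 but stayed to Week 152, who are a selected group.
- **Week 104 drawn.** The Week 152 value loses to the closer record and appears in no by-visit summary, although the SAP promises lipid, laboratory and vital-sign summaries at each planned visit.

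At stake are the by-visit Week 104 figures and the by-visit picture of the year that Amendment 5 added to characterise safety over three years.

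**Working it through.** **1. Reproduce the SAP's boundaries.** The lower limits are midpoints of adjacent scheduled weeks, 7 × (w1 + w2) / 2:

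- labs, Weeks 96 and 104: 7 × 200 / 2 = 700
- vital signs, Weeks 102 and 104: 7 × 206 / 2 = 721
- HbA1c, weight and hsCRP, Weeks 48 and 104: 7 × 152 / 2 = 532
- HbA1c, Weeks 60 and 104: 7 × 164 / 2 = 574

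All four match Appendix A, so the convention is clear.

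**2. Target days (7 × week + 1).** Week 104 = Day 729, Week 116 = 813, Week 128 = 897, Week 140 = 981, Week 152 = 1065. With the protocol's ±7 days, Week 104 draws fall on Days 722–736 and Week 152 draws on Days 1058–1072.

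**3. Apply the rule to example subjects (lipids).**

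- Draws on Days 589 and 1065, none at Week 104: the only record after Day 700 is Day 1065, so it becomes Week 104. It is 1065 − 729 = 336 days late. Within the visit window the range is 1058 − 729 = 329 to 1072 − 729 = 343 days.
- Draws on Days 729 and 1065: Day 729 is kept, and Day 1065 has no row.
- Draws on Days 736 and 1058: Day 736 is kept, with the same result for the later draw.

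For vital signs, a missed Week 104 would first be filled from Week 116, 813 − 729 = 84 days late.

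**4. Close the windows by the same convention.**

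- Weeks 104 and 152: 7 × 256 / 2 = 896
- Weeks 104 and 116: 7 × 220 / 2 = 770
- Weeks 116 and 128: 7 × 244 / 2 = 854
- Weeks 128 and 140: 7 × 268 / 2 = 938
- Weeks 140 and 152: 7 × 292 / 2 = 1022

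With a laboratory cap at Day 896, all draws on Days 722–736 map to Week 104 and all draws on Days 1058–1072 map to Week 152.

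**5. Related mismatch in the same table.** The laboratory rows use Weeks 72 and 96, but the current protocol draws at Week 84 (Day 589, window 582–596). As printed, the rows are (420, 588) and (588, 700]. Days 582–587 therefore go to Week 72, Days 589–596 go to Week 96, and Day 588 goes to neither. With Week 84 as the preceding draw, the midpoint lower limit for Week 104 would be 7 × (84 + 104) / 2 = 658 rather than 700.

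**The case against.** The strongest answer is scope. SAP Section 1 describes an interim plan for regulatory filings and cites protocol Amendment 2 of 30 April 2013. By the protocol's amendment history, Amendment 1 had cut the study to two years, and the third year arrived only with Amendment 5 on 19 December 2014. Week 104 was then the last window, and leaving it open was ordinary practice. The SOC group itself dates from Amendment 1 (12 February 2013). A subject randomised against SOC on that date would reach Day 1065 in January 2016, and the SAP's cutoff may well be much earlier. All of this stands. A reader might infer that the sponsor's current plan already reports Week 152 values as Week 104. The documents do not show that: the cutoff date is not given, and no final-analysis SAP is among them.

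Three further limits also stand:

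- A reader might infer that third-year data are thrown away. Only by-visit summaries are affected. Worst-shift tables, CK and liver-test incidence, antibodies at any time, adverse events and exposure all run to end of study or cutoff and would use them.
- A missing Week 104 visit is not enough by itself. An unscheduled or early-termination draw that lies after the lower limit and closer to Day 729 would be chosen instead.
- Week 104 LDL-C as a named endpoint, estimated with a mixed effects model, is the protocol's. The interim SAP summarises LDL-C descriptively at each planned lipid visit. The documents do not show that these windows govern the protocol's Week 104 estimate.

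The objection does not remove the point. The SAP excludes no third-year data by rule, sets no cutoff date, and is the only analysis plan supplied.

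**Conclusion.** The point holds conditionally. Applied as written to a cutoff that includes data after Week 104, Appendix A mislabels a Week 152 laboratory record as Week 104 by about 336 days (329 to 343 for an in-window visit) whenever no closer record follows the lower limit. It leaves Weeks 116 to 152 without a row in any by-visit table. For a cutoff before any subject passes Week 104 it has no effect.

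The number of subjects affected cannot be computed. It equals those who lack a closer record near Week 104 but attend a later visit that collects the measurement, and the documents give no missed-visit rate. The conclusion rests on one assumption, that the windows are reused without revision. It is a version gap between an interim SAP and a later protocol, to be closed before third-year data are analysed. It is not evidence of an error in a completed analysis.

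**What to change.** Before any analysis that includes data after Week 104, bring Appendix A into line with the current protocol schedule, using the SAP's own midpoints:

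- **Lipids, chemistry, hematology, antibodies, HbA1c, weight:** cap Week 104 at Day 896 and add Week 152 as > 896.
- **Vital signs:** Week 104 (721, 770], Week 116 (770, 854], Week 128 (854, 938], Week 140 (938, 1022], Week 152 > 1022.
- **ApoA1, ApoB, Vitamin E, urinalysis, microalbumin, hsCRP:** cap Week 104 at Day 896 and add no Week 152 row, because these are not scheduled then. Most of them share a column with the lipids at present, so that column must be split.
- **In the same edit,** reconcile the Week 72 and Week 96 laboratory rows with the protocol's Week 84 draw. This also resets the lower limit of Week 104 for those tests and settles Day 588.

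The cost is an appendix edit and an update to the derivation program. Sites do nothing, and results from cutoffs taken before any subject passes Week 104 are unaffected by the new caps and third-year rows.
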